11.5.2.5 Missing Data

Missing data will be recorded as they are, and there will be no imputation of missing values.

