3 STUDY DESIGN

This is a phase 1, double-blind, randomized clinical trial to evaluate the safety, tolerability, and immunogenicity of single-vial lyophilized ID93 + GLA-SE compared to the two-vial presentation consisting of lyophilized ID93 and liquid GLA-SE administered as two IM injections in healthy adult subjects (aged 18 - 55).

The two treatment groups are outlined in Table 1. Subjects will receive a total of two doses administered IM on Days 0 and 56. Subjects will be monitored for approximately 421 days (one year following the last study injection), including safety laboratory analyses done just prior to and 7 days following each study injection. Tears and nasal swabs will be obtained for exploratory antibody analysis at Days 0, 70, and 224. Blood samples will be obtained for immunological assays (secondary and exploratory) at Days 0, 7, 14, 56, 63, 70, 84, and 224).

Table 1: Treatment Assignments

Treatment Group	N	Treatment Assignment	Timing of Study Injections
1	25	ID93 (2 µg, lyophilized) + GLA-SE (5 µg, liquid) [two-vial presentation]	Days 0 and 56
2	23	ID93 + GLA-SE (2 µg ID93, 5 µg GLA) [lyophilized, single-vial]	Days 0 and 56

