7.2 Plan for Statistical Summaries and Analyses

7.2.1 General Considerations

Statistical summaries and analyses of baseline and safety data will be provided for the safety population, defined as all subjects who receive at least one study injection. Summaries and analyses of immune response data will be provided for the per-protocol population. The objectives of the immune response statistical summaries and analyses are to assess the immunogenicity following intramuscular administration of study vaccine among the treatment groups. The goals are:

1. To describe the humoral and cellular response to both vaccine presentations in terms of magnitude and positive response rate
2. To determine if there is a significant difference in the immune response elicited by the two-vial and the single-vial lyophilized vaccine presentation

All individual subject data listings will be provided in appendices to the clinical study report. Data will be summarized and tabulated by treatment group and descriptive statistics will be provided where

appropriate. The immunology analysis will be performed using either SAS version 9.3 or higher or R version 3.5 or higher.

Categorical data will be analyzed using Fisher's exact test using 0.05 level of significance ($\alpha = 0.05$) with Holm-Bonferroni adjustments whenever pairwise comparisons are made between more than two categories.

Continuous data will be compared between two treatment groups using a Two-sample T-test if the normality assumption is met or Wilcoxon Rank-Sum Test, otherwise. Response rates will be compared using a Fisher's Exact test. Significant differences will be detected based on a two-sided test with $p \leq 0.05$ ($\alpha = 0.05$). Comparisons will be accompanied by the point-estimate and 95% CI for each group.

Missing data: The analysis plan assumes that missing data are missing completely at random (MCAR) and analysis will be performed on the available data.

Individual subject data listings will be provided as separate appendices in the CSR. All summaries, statistical analyses, and individual subject data listings will be analyzed by using either SAS version 9.3 or higher or R version 3.5 or higher.

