7.2.3.2.1 ICS

PBMC ICS will be performed on Days 0, 7, 14, 56, 63, 70, 84, and 224 to determine the proportion of single and multi-functional CD4 and CD8 T-cells producing various combinations of IFN- γ , TNF, IL-2, IL-4, IL-21, and CD154 in response to ID93 stimulation. A gate is applied for each functional marker, not accounting for co-expression of other markers. Boolean gates are later created based on the gates shown to identify cells expressing various combinations of markers. We will analyze the T cell population “Any Two”, which are positive for at least two immune markers among IFN- γ , TNF, IL-2, IL-4, IL-21, and CD154. We will also evaluate T cells that express selected combinations of the six immune markers. The selected combinations will be indicated in the data set. Any negative background-subtracted values will be set to zero.

The following **listing** is planned to be presented:

- Cellular Response: PBMC ICS: T cell Response
 - Percent immune marker-positive (“Any Two” and for selected combinations of the six), background-subtracted cytokine response, change from baseline, fold change from baseline, and responder status

Tabular summaries will present “Any Two” immune marker-positive and polyfunctional responses (only background-subtracted non-zero values will be presented). T-cell response frequencies will be summarized by treatment regimen. Percentages will be based on the total number of subjects within each treatment group. The following **tables** are planned for presentation:

- Cellular Response: PBMC ICS: T cell Response and Change from Baseline
 - Percent immune marker-positive background-subtracted T cell response (“Any Two” and for selected combinations of the six) and change from Baseline, including N, Median, and 95% CI for each parameter.
- A Narrative Table will be prepared and will include
 - Medians of the “Any Two” CD4 and CD8 T cell responses per treatment group and study visit with p-value of the statistical comparison of the treatment groups

- Responder Rate of the “Any Two” CD4 and CD8 T cell responses per treatment group and study visit with p-value of the statistical comparison of the treatment groups

The following **figures** are planned:

- Cellular Response: PBMC ICS: T Cell Response Magnitude by Study Day
 - Background-subtracted total T cell subject response (“Any two”) by visit and by T cell type.

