 - This figure is also to include on separate pages the DMSO values as well to illustrate background for T cell results.
 - This is to be a **box and dot plot** of the background-subtracted with negative values set equal to zero ‘Any two’ with background-subtracted (or background values) values (y-axis) at each visit (x-axis) (study days plotted next to each other on one page). Box plots summarize by treatment group and dots represent individual values. The median values per treatment group are to be presented by means of a horizontal line, boxes outline first to third quartiles, and whiskers represent minimum to maximum values.
 - Different symbols are to be used to differentiate between responders (closed circles), non-responders (cross) and missing responder status (triangle).
- Cellular Response: PBMC ICS: Polyfunctional Profile Plot in CD4 and CD8 T Cells
 - Background-subtracted polyfunctional plot in T cells (selected combinations of IFN- γ , TNF, IL-2, IL-4, IL-21, and CD154) by visit and T cell type.
 - Separate pages for each visit day are to be prepared.
 - This is to be a **dot plot** of the background-subtracted single-gate T cell response (y-axis) versus each selected immune marker combination available (excluding where all included cytokines are negative) (x-axis).
 - The background-subtracted ANY TWO cytokine response in T cells is to be presented as a subplot on the right hand side.

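### The SAP bases ICS response percentages on all subjects in the arm, so a missing ICS result counts arithmetically as non-response; the denominator of the Fisher test is not stated

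*SAP*

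**What the plan says.** SAP 7.2.3.2.1 introduces the ICS tables with "T-cell response frequencies will be summarized by treatment regimen" and then fixes the denominator: "Percentages will be based on the total number of subjects within each treatment group". The same section plans a narrative table with the responder rate for the Any Two CD4 and CD8 "T cell responses per treatment group and study visit with p-value of the statistical comparison of the treatment groups".

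Three other places bear on this:

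- SAP 7.2.1 assumes data are missing completely at random and says "analysis will be performed on the available data". It also names a two-sided Fisher's exact test at 0.05 for response rates, and the per-protocol population for immune-response summaries.
- SAP 5 defines per-protocol as eligible, randomized and given both assigned injections. It does not require a valid assay result.
- The ICS figure in SAP 7.2.3.2.1 uses separate symbols for "non-responders (cross) and missing responder status (triangle").

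**The concern.** A percentage over everyone in the arm gives a subject with a failed sample, poor cell recovery or a missed visit the same weight as a subject who was assayed and did not respond. The general rule in SAP 7.2.1 would leave that subject out at that visit. A programmer could defend either denominator, and the two give different tables.

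The protocol (2.2) calls this a bridging study, and the second immune-response goal in SAP 7.2.1 is to determine whether the presentations differ significantly. ICS responder rates are compared at many visits, for CD4 and for CD8. If one arm loses more samples, its percentage falls for reasons unrelated to the vaccine. If the Fisher test uses the same denominator, the p-value is affected too. If the test uses evaluable subjects instead, the table prints a percentage and a p-value that rest on different subjects.

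**Working it through.** The plan states no figure that depends on this denominator, so there is nothing to reproduce. The check measures what the literal rule would do.

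**Inputs from the documents.** Arms of 25 (two-vial) and 23 (single-vial), SAP Table 1; two-sided Fisher's exact test, significant at p ≤ 0.05, SAP 7.2.1.

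**Assumptions.** Responder rates and missing counts are not in the documents and are varied below. The calculation takes the full arms as N, although the per-protocol arms may be smaller. It also assumes that the test uses the total-N denominator, which the SAP does not say.

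**Effect on the percentage.** With N subjects, m missing and true rate p among assayed subjects, the expected percentage is p(N − m)/N. For p = 80% and m = 3 of 23: 0.80 × 20/23 = 69.6%, against 80% on evaluable subjects. Each missing result in the arm of 23 costs p/23, which is 2.2 points at p = 50% and 3.9 points at p = 90%.

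**Effect on the test, same true rate in both arms.** Responders are X1 ~ Bin(25, p) and X2 ~ Bin(23 − m, p). The false-positive rate is the summed probability of all (X1, X2) with Fisher p ≤ 0.05. The total-N version tests X1/25 v X2/23; the evaluable version tests X1/25 v X2/(23 − m). Nobody is missing in the arm of 25.

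| True rate | Missing of 23 | Expected percentages, total N | False-positive, total N | False-positive, evaluable |
|---|---|---|---|---|
| 50% | 0 | 50.0 v 50.0 | 4.0% | 4.0% |
| 50% | 3 | 50.0 v 43.5 | 5.5% | 3.5% |
| 50% | 5 | 50.0 v 39.1 | 9.3% | 3.0% |
| 80% | 0 | 80.0 v 80.0 | 3.5% | 3.5% |
| 80% | 3 | 80.0 v 69.6 | 8.4% | 2.9% |
| 80% | 5 | 80.0 v 62.6 | 18.4% | 2.6% |
| 90% | 0 | 90.0 v 90.0 | 2.4% | 2.4% |
| 90% | 3 | 90.0 v 78.3 | 14.2% | 1.7% |
| 90% | 5 | 90.0 v 70.4 | 33.5% | 1.4% |

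With 0 v 1 missing, the total-N rate does not exceed 4.2% for true rates from 50% to 90%.

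**Boundary case.** Every assayed subject responds and 4 of 23 are missing: 19/23 (82.6%) v 25/25 gives p = 0.0455. On evaluable subjects, 19/19 v 25/25 gives p = 1. With 3 missing, 20/23 v 25/25 gives p = 0.102. If only the arm of 25 has missing results, 5 missing gives p = 0.0507 and 6 gives p = 0.023.

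**Equal chance of a missing result.** If each result is missing with probability q in both arms, unrelated to response, responders are Bin(N, p(1 − q)) in each arm and the total-N test is valid. For p from 50% to 90% and q from 5% to 20%, the false-positive rate is 3.2% to 4.0%. The percentages are still too low: at p = 80% and q = 10% both arms are expected to show 0.80 × 0.90 = 72%.

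**The case against.** The strongest reply is that the sentence is loose wording and not a settled rule. No passage says that a subject without a result is classified as a non-responder, SAP 7.2.1 prescribes available-data analysis, and the denominator sentence mentions neither the Fisher test nor the narrative table. This stands in part: the test denominator is unstated, not fixed at total N. But the sentence is specific to ICS and 7.2.1 is general, so following the sentence is a reasonable reading.

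Immune summaries are also per-protocol, so total subjects may mean fewer than 25 and 23, and subjects given one injection are already excluded. That is correct, but per-protocol status does not require a valid assay, so lost samples and missed visits remain.

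The larger error rates need a lopsided split and a high response rate. This stands too. With a 10% chance of missing in both arms, 0 of 25 together with at least 4 of 23 has probability of about 1.4%. The study is also not designed to test a formal hypothesis (Protocol 11.3), and the SAP's listed ICS endpoints are cell proportions and polyfunctionality, with responder rate an added comparison. The ICS table does report N, but it is to present only non-zero values, so that N may not be the number assayed.

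A reader might infer two further things that the documents do not support:

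- That the rule contradicts the protocol, where 11.5.2.5 says "there will be no imputation of missing values". That subsection belongs to the safety analysis; immunology is 11.5.3.
- That the triangle in the ICS figure shows that the SAP expects absent samples. The dots are individual values, so a triangle most naturally marks a subject with a plotted value but no responder status, for example without a baseline. It shows only that missing status is kept apart from non-response.

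**Conclusion.** The denominator sentence is wrong as written. Followed literally, it understates the ICS response percentage in any arm with a missing result, and it conflicts with SAP 7.2.1. That holds whatever the amount of missingness.

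The effect on the comparison between presentations is conditional. It requires unequal missingness and a Fisher test on the total-N denominator. Under those assumptions, with arms of 25 and 23, it ranges from negligible (one extra missing result) to a false-positive rate of 9% to 34% with 0 v 5 missing at true rates of 50% to 90%. A reader might infer that the plan will produce a false difference between the vaccines. The documents do not support that, because they report no ICS missingness and do not state the test denominator. This should be corrected, but it does not by itself invalidate the immunogenicity comparison.

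**What to change.** Replace the sentence in SAP 7.2.3.2.1 with: *ICS responder percentages and Fisher tests at each visit use per-protocol subjects whose ICS responder status can be determined at that visit (valid ICS results at Day 0 and at that visit); the numbers evaluable and missing are shown by arm and visit.* Apply the same denominator to the narrative table. Counting missing results as non-response may be kept as a sensitivity analysis.

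The new sentence depends on a definition of ICS responder status. SAP 7.2.3.3 gives rules headed for ELISA and ELISpot but none for ICS, so state that rule, or state that the ELISpot rule applies, in the same edit.

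The cost is one replaced sentence, the ICS responder statement and extra table rows for the counts. No new data are needed. Intervals widen slightly where results are missing.

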7.2.3.2.2 ELISpot

IFN- γ and IL-10 ELISpot will be performed on Days 0, 14, 56, 70, 84 and 224 to determine the proportion of PBMCs producing IFN- γ or IL-10 in response to stimulation with ID93 or unstimulated (PBS).

The following **listing** is planned to be presented:

- By treatment group, each participant’s ELISpot response will be listed, including: Subject ID, Analyte, Stimulation condition, Visit Day, SFU-Background Scaled Result/ $<0 = 0$ (SFU/ 10^6 PBMC), Change from Baseline, and Responder Status (Yes/No).

The following **tables** are planned for presentation (repeat each table for IL-10):

- PBS-subtracted antigen-specific IFN- γ ELISpot response (SFU/ 10^6 PBMC), change from Baseline, and Responder Status
 - This is to include descriptive statistics and 95% CI for the median for each visit and stimulation antigen.
 - Responder status is determined by the SCHARP method described in Section 7.2.2.3.
- A Narrative Table will be prepared and will include
 - Medians of the responses per treatment group and study visit with p-value of the statistical comparison of the treatment groups
 - Responder Rate of the IFN- γ responses per treatment group and study visit with p-value of the statistical comparison of the treatment groups

The following **figure** is planned for presentation (repeat figure for IL-10):

- PBS-subtracted IFN- γ ELISpot subject response (SFU/10⁶ PBMC) by visit.
 - This is to be a box and dot plot of the DMSO-subtracted SFU/10⁶ PBMC values (y-axis) at each visit (study days plotted next to each other on one page) per stimulation antigen (each stimulation antigen on a separate page, including DMSO). The median values per treatment group are to be presented by means of a horizontal line, boxes outline first to third quartiles, and whiskers represent minimum to maximum values.
 - Different dot symbols are to be used to differentiate between responders and non-responders (e.g., open vs closed symbols).

7.2.3.3 Defining Cut-Offs for Reactivity and Responder Rates

The resultant titer determination from assay of serum IgG is normalized to internal standards that are run on every plate in the low, middle, and high portions of the assay's dynamic range as well as multiple negative control samples. Values from control samples must be within established range for the plate to pass and for a valid endpoint titer determination. A qualification of the total IgG ELISA assay indicated that a Post:Pre Ratio of 4 for the antibody assay (IgG) is an appropriate cut-off value for distinguishing responders and non-responders.

ELISA responder rates are determined as follows. To determine the responder status (per subject and visit): If the calculated fold change (Post:Pre Ratio) is greater than or equal to 4, the subject is to be considered a responder at that specific post-Baseline visit. If the calculated fold change is less than 4, the subject is to be considered a non-responder at that specific post-Baseline visit. If the measured MEPT is below the limit of detection (LOD), the sample is assigned the LOD value.

ELISpot responder rates are determined using the method as follows:

- ELISpot responses per stimulation condition are provided.
- These results are then compared at each visit and stimulation antigen, using the Fisher's EXACT test.
- P-values are then to be adjusted for multiplicity, if necessary
- If both the DMSO and the active antigen values are below 27 SFU/10⁶ PBMC, the result is to be regarded as non-responder. If the stimulation value is above 27 and the DMSO value is below 27, the normal procedure should follow to determine the responder status.
- Step 1: Determine whether the number of cells responding to the active antigen stimulation is statistically significantly more than the number of cells responding to DMSO stimulation at Baseline (Study Day 0).
 - One-sided adjusted p-value ≥ 0.05 indicates that the number of cells responding to the active antigen stimulation is not statistically more than the number of cells responding to the DMSO stimulation.
 - Subject is classified as a non-responder at Baseline (Study Day 0).
 - One-sided adjusted p-value < 0.05 indicates that the number of cells responding to the active antigen stimulation is statistically more than the number of cells responding to the DMSO stimulation.
 - Subject is classified as a responder at Baseline (Study Day 0).
- Step 2: Determine whether the number of cells responding to the active antigen stimulation is statistically significantly more than the number of cells responding to DMSO stimulation at Study Day 14, 56, 70, 84, and 224 respectively.

- o One-sided adjusted p-value ≥ 0.05 indicates that the number of cells responding to the active antigen stimulation is not statistically more than the number of cells responding to the DMSO stimulation.
 - Subject is classified as a non-responder at the relevant post-Baseline visit.
- o One-sided adjusted p-value < 0.05 indicates that the number of cells responding to the active antigen stimulation is statistically more than the number of cells responding to the DMSO stimulation.
 - Subject is classified as a responder at the relevant post-Baseline visit.

- Determine the responder status post-Baseline when taking Baseline (Study Day 0) into account:

Baseline (Determined in Step 1)	Each post-Baseline visit (Determined in Step 2)	Responder Status
Non-responder	Non-responder	Non-responder
Non-responder	Responder	Responder
Responder	Non-responder	Non-responder
Responder	Responder	Determine responder status by means of the odds ratio

- Determine the odds ratio for results at Baseline (Study Day 0). If the DMSO positive count is zero, the odds ratio will be undefined. In these cases the positive DMSO count should be imputed to 1 in order to determine an odds ratio.
- Determine the odds ratio for results at post-Baseline visits. If the DMSO positive count is zero, the odds ratio will be undefined. In these cases the positive DMSO count should be imputed to 1 in order to determine an odds ratio.
- Perform the Breslow-Day test:
 - o Test for homogeneity of odds ratios at each relevant post-Baseline visit and Baseline (Study Day 0).
 - o P-value ≥ 0.05 indicates that the odds ratio at Baseline (Study Day 0) and each post-Baseline visit do not differ statistically significantly.
 - Subject classified as a non-responder at the relevant post-Baseline visit.
 - o P-value < 0.05 indicates that the odds ratio at Baseline (Study Day 0) and each post-Baseline visit differ statistically significantly.
 - Difference in log odds ratio should be evaluated in order to determine the responder status at the relevant post-Baseline visit.
- Calculate the difference in the log of the odds ratios at each relevant post-Baseline visit and Baseline (Study Day 0).
 - o Difference in log odds ratio = $\log(\text{odds ratio at Study Day } x) - \log(\text{odds ratio at Baseline [Study Day 0]})$.
- Determine the responder status based on the Breslow-Day and difference in log odds ratio for cases where the Baseline (Study Day 0) and relevant post-Baseline visit was determined as responders:

Breslow-Day test p-value	Difference in log odds ratio	Responder status
≥ 0.05	<0	Non-responder
≥ 0.05	>0	Non-responder
<0.05	<0	Non-responder
<0.05	>0	Responder

The aforementioned steps are to be implemented to determine the data record-level response per subject and stimulation antigen (excluding DMSO) and visit. In order to determine the response per

subject at a day-level, and therefore across T cell type and stimulation antigen, the following conventions are to be used:

- Per subject and visit, if all records have a record-level responder status of non-responder, the day-level responder status is determined as a non-responder.
- Per subject and visit, if at least one of the records has a record-level responder status of responder, the day-level responder status is determined as responder.

The overall responder status is determined as a single responder status per subject across T cell types, stimulation antigens and visit and the following conventions are to be used to determine the overall responder status:

- Per subject, if all days have a day-level responder status of non-responder the overall responder status is determined as non-responder.
- Per subject, if at least one of the days has a day-level responder status of responder, the overall responder status is determined as responder.

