Appendix 2: Schedule of Blood Draws and Volumes

	Screen	Day 0	Day 7 (±1)	Day 14 (±3)	Day 56 (±3)	Day 63 (±1)	Day 70 (±3)	Day 84 (±5)	Day 224 (±10)
Serum chemistry and hematology	12.5		12.5			12.5			
HIV 1/2, HBsAg, HCV	12								
QuantiFERON®-TB Gold	3								
Serum IgG		6*		4	4		4	4	4
MGIA		4					4		4
PBMC**		64	24	64	64	24	64	64	64
Blood volume per visit	27.5	74	36.5	68	68	36.5	72	68	72
Cumulative total volume	27.5	101.5	138	206	274	310.5	382.5	450.5	522.5

Note: blood volumes are approximate and may be adjusted for clinical site requirements

* Includes 2 mL for serum to be banked for autoimmune testing, if indicated

** PBMC utilized in ICS and ELISpot will be left unstimulated or stimulated with ID93 protein or overlapping peptides pools encompassing the individual vaccine antigens (Rv1813, Rv2608, Rv3619, Rv3620), or a positive control (SEB). PBMC used in B cell ELISpot will be left unstimulated or stimulated with ID93 protein, SEB, or polyclonal stimulation reagents.

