7.2.3 Immune Response

The following are the endpoints of interest:

Primary Analysis Endpoints:

- IgG antibody responses to ID93 by ELISA at Days 0, 14, 56, 70, 84, and 224
 - Mean endpoint titer of ID93-specific antibodies for total IgG on for each treatment group.
 - The proportion of subjects with at least a 4-fold increase in ID93-specific IgG antibody levels on Days 14, 56, 70, 84, and 224 relative to baseline (Day 0).
 - Mean fold change from baseline (Day 0) in IgG antibody responses to ID93.
- T cell responses to ID93 by PBMC ICS on Days 0, 7, 14, 56, 63, 70, 84, and 224
 - The proportion of cells expressing any two of IFN- γ , TNF, IL-2, IL-4, IL-21, or CD154 in response to ID93.
 - The polyfunctionality based on expression of IFN- γ , TNF, IL-2, IL-4, IL-21, or CD154.
- T cell responses to ID93 by ELISpot on Days 0, 14, 56, 70, 84 and 224
 - The number of IFN- γ cytokine-secreting cells in PBMC samples in response to the ID93 antigen relative to baseline (Day 0) at Days 14, 56, 70, 84, and 224, as assayed by ELISpot.

Secondary and Exploratory Analysis Endpoints:

- IgG subclass antibody responses to ID93 by ELISA at Days 0, 14, 56, 70, 84, and 224

- The proportion of subjects with at least a 4-fold increase in ID93-specific IgG1, IgG2, IgG3, and IgG4 antibody levels on Days 14, 56, 70, 84, and 224 relative to baseline (Day 0).
- Mean endpoint titer of ID93-specific antibodies for IgG1, IgG2, IgG3, and IgG4 on for each treatment group.

Immune responses for each treatment group will be evaluated by calculating the response rate and magnitude of response to ID93 at all timepoints for each immunologic endpoint. Comparisons of response rates for IgG and cytokine responses between treatment groups will be made using Fisher's exact tests.

The magnitude of IgG and cytokine responses will be compared between treatment groups using a Two-sample T-test if normality assumption is met or Wilcoxon Rank-Sum Test, otherwise.

Percentages of CD4+ cells producing selected immune markers will be summarized by time point and compared between treatment groups.

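### The visit-level ELISpot responder rule pools all stimulations except DMSO, while the endpoint and Tables 12-13 concern ID93; the SAP should tie responder status to the ID93 record and keep SEB out

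*SAP*

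**What the plan says.** SAP 7.2.3 defines the ELISpot endpoint as the count of cytokine-secreting cells "in response to the ID93 antigen relative to baseline (Day 0) at Days 14, 56, 70, 84, and 224, as assayed by ELISpot". Narrative Tables 12 and 13 (SAP 7.4) carry the IFN-γ and IL-10 results under titles that name the response to ID93. SAP 7.2.3.2.2 puts into the narrative table a responder rate and the medians of the "responses per treatment group and study visit with p-value of the statistical comparison of the treatment groups".

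SAP 7.2.3.3 builds responder status in layers. Its steps are used "to determine the data record-level response per subject and stimulation antigen (excluding DMSO) and visit". It then forms one status for the "subject at a day-level, and therefore across T cell type and stimulation antigen, the following conventions are to be used": a subject is positive for the visit "if at least one of the records has a record-level responder status of responder, the day-level responder status is determined as responder". DMSO is the only condition named as left out.

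The documents differ on which conditions are run. The footnote to Protocol Appendix 2 covers both ICS and ELISpot and lists unstimulated cells, ID93 protein, "overlapping peptides pools encompassing the individual vaccine antigens (Rv1813, Rv2608, Rv3619, Rv3620), or a positive control (SEB"). SAP 7.2.3.2.2 names only ID93 and PBS for ELISpot. The same section nevertheless lists results by stimulation condition, tabulates them by stimulation antigen, and gives each antigen its own figure page. For the responder method it points to Section 7.2.2.3, which is the reactogenicity section; the method is in 7.2.3.3.

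On multiplicity, the set-up in 7.2.3.3 says "P-values are then to be adjusted for multiplicity, if necessary". Steps 1 and 2 then decide on a one-sided adjusted p-value at 0.05. No method or family is named, and no adjustment is stated for the Breslow-Day test.

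**The concern.** The pooled visit status answers a different question from the endpoint. It asks whether anything in the stimulation panel was positive, not whether the ID93 stimulation was. Each extra condition gives a true non-responder another chance of a positive call, and how far that is controlled depends on an adjustment the SAP does not define.

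SEB is a separate matter. A positive control should be positive on Day 0 and at later visits, so it falls in the row of the table where both are responders. There, a Breslow-Day p-value below 0.05 with a higher odds ratio than on Day 0 yields a responder. A stronger SEB well or a lower control count could produce that without any vaccine effect, and adjusting the Step 1 and 2 p-values would not prevent it.

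At stake is the responder rate in each arm and the Fisher comparison between them. Protocol 2.2 calls the trial a bridging study, and SAP 7.2.1 sets out to find whether the two presentations differ. False calls added to both arms raise both rates and make the presentations look more alike.

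**Working it through.** The documents state no false-call rate for ELISpot, so there is no planned figure to reproduce.

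**Inputs from the documents.** Any-positive rule within a visit; one-sided 0.05 per record; the 27 SFU per million floor; the Day 0 by later-visit table and the Breslow-Day step (all SAP 7.2.3.3). Number of vaccine-antigen conditions k: 5 under Protocol Appendix 2 (ID93 plus four pools), or 1 if only ID93 is run (SAP 7.2.3.2.2). Arms of 25 and 23 (SAP Table 1).

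**Assumptions.** Poisson counts per million cells; background of 5-60 SFU for the antigen calculation; SEB at 500-1500 SFU with background of 3-30 SFU; between-visit CV for SEB of 0-0.5. The documents give none of these.

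**Step 1: upper bound.** With independent, unadjusted tests, P(at least one positive) = 1 − (1 − 0.05)^k. For k = 5 this is 1 − 0.95^5 = 0.226. Equicorrelated normal statistics give 0.166 at correlation 0.5 and 0.117 at 0.8. This step ignores the floor and the Day 0 table.

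**Step 2: the SAP's own algorithm.** 200,000 simulated subjects with no true response, a shared DMSO control, the 27 SFU floor, the Day 0 table, and a Wald form of the Breslow-Day test. Bonferroni (0.05/5) is applied to Steps 1 and 2 only.

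| Background (SFU) | ID93 alone | Five, unadjusted | Five, Bonferroni |
|---|---|---|---|
| 5-10 | 0.000 | 0.000 | 0.000 |
| 20 | 0.0188 | 0.0845 | 0.0215 |
| 30 | 0.0367 | 0.1261 | 0.0279 |
| 40 | 0.0373 | 0.1287 | 0.0298 |
| 60 | 0.0396 | 0.1345 | 0.0319 |

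Unadjusted pooling multiplies the rate by 0.1345/0.0396 = 3.4 to 0.0845/0.0188 = 4.5 at backgrounds of 20-60, and adds nothing at 5-10.

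**Step 3: SEB, if its records are kept.** The chance per visit of a responder call through the Breslow-Day step, with no vaccine effect and Poisson background, is 0.002-0.024 at CV 0, 0.016-0.147 at CV 0.3 and 0.041-0.235 at CV 0.5. With overdispersed background it reaches 0.296.

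**Step 4: effect on the comparison.** If a fraction f of true non-responders is called positive, the observed rate is p + (1 − p)f. For illustrative true rates of 0.80 and 0.40 and f = 0.13, these become 0.80 + 0.20 × 0.13 = 0.826 and 0.40 + 0.60 × 0.13 = 0.478. The difference shrinks from 0.400 to 0.348. Power of the two-sided Fisher test at 0.05, by exact enumeration:

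| f | 0.80 vs 0.40 | 0.40 vs 0.10 |
|---|---|---|
| 0 | 0.78 | 0.63 |
| 0.085 | 0.71 | 0.49 |
| 0.13 | 0.67 | 0.44 |

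When the arms share one rate, the Fisher test's type I error is 0.034 at a rate of 0.2262 and 0.040 at 0.5, so it stays below 0.05.

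**The case against.** Several arguments on the other side carry weight.

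- **The error is not simply uncontrolled.** A reader might infer that from the any-positive rule. Steps 1 and 2 require an adjusted p-value, and with Bonferroni the pooled rate (0.022-0.032 at backgrounds of 20-60) is close to that of ID93 alone (0.019-0.040). What remains is that method and family are unnamed and the Breslow-Day step has no stated adjustment.
- **A positive pool is not a false ID93 response.** The pools cover the four proteins fused in ID93 (Protocol 6.1). Counting them changes the endpoint definition and adds chances of a positive; it does not turn real component responses into errors.
- **SEB entry is an inference.** Appendix 2 calls it a positive control, and the steps in 7.2.3.3 speak of the active antigen, which can be read as excluding it. If it is kept, it is not a responder by default: the odds ratio must rise significantly. But DMSO is the only written exclusion, so literal programming would retain any SEB records supplied.
- **The pools may not be run.** SAP 7.2.3.2.2 names only ID93 and PBS, so k may be 1, in which case the rule has no effect. The mention of T cell type, which does not apply to a PBMC ELISpot, suggests text carried over from another assay.
- **The link to Tables 12 and 13 is not stated.** Their titles make the ID93 record a natural reading. The SAP does not confirm it, and the only visit-level status it defines is the pooled one.
- **The trial was not sized for power** (SAP 7.1) and tests no formal hypothesis (Protocol 11.3). The power figures therefore illustrate dilution and are not a shortfall against a target.

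**Conclusion.** The concern holds as a mismatch between rule and endpoint, worth correcting because the correction is cheap. Read literally, SAP 7.2.3.3 lets records other than ID93 decide a status that may be reported as the response to ID93.

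The size is conditional. If the pools are run and the pooled status is reported, the false visit-level rate is about 0 to 0.13 unadjusted, with 0.23 as the independent-test bound, and about 0.02-0.03 with Bonferroni at backgrounds of 20-60 SFU. ID93 alone gives about 0 to 0.04. SEB could add near 0 to about 0.24 with Poisson background. These ranges depend on background, SEB counts and visit variability that the documents do not give.

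The harm is overstated responder rates and a diluted difference between presentations. A reader might infer that the rule raises the risk of a spurious between-arm difference. It does not, because it applies identically to both arms and the Fisher test keeps its level. If ELISpot is run with ID93 only, nothing changes.

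**What to change.** In SAP 7.2.3.3, replace the day-level convention with wording to this effect: the ELISpot responder status at a visit, as reported in Tables 12 and 13, is the record-level status for the ID93 protein stimulation, determined separately for IFN-γ and IL-10. Peptide-pool results are reported by pool as descriptive. SEB and negative-control wells serve assay validity only and never enter responder status.

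If an any-antigen status is kept as a supplementary summary, limit it to ID93 and the four pools. Replace the conditional adjustment with Holm across those five conditions at each visit, applied to both the Fisher and the Breslow-Day p-values. In 7.2.3.2.2, list the stimulations actually run and correct the cross-reference to the responder method.

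The cost is a few sentences and a filter on stimulation condition in the program, with no new data. The small downside is that subjects positive only to a pool leave the headline rate, which may fall slightly.
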